10.4 Per Protocol and Intent to Treat Analyses

Analyses of the primary and secondary effectiveness endpoints will be conducted on the intent-to-treat (ITT) population and the per-protocol (PP) population at each specified study interval defined as follows:

PP Population: [REDACTED]

ITT Population: [REDACTED]

[REDACTED]

[REDACTED]

11.0 Study Monitoring

11.1 Training

SPR Therapeutics or their designee will conduct a Site Initiation and Training Visit prior to initiation of the study. The purpose of this visit will be to develop a common understanding of the clinical protocol, Case Report Forms (CRFs), study specific procedures, Investigator Responsibilities, and Good Clinical Practices (GCPs) among the clinical research monitors and the Investigational Site team.

11.2 Routine Monitoring

Monitoring visits to the Investigational Site will be conducted periodically, as determined by the rate of subject enrollment, during the study to ensure that the most currently approved version of the Investigational Plan is being followed and that the site is in adherence with all Good Clinical Practices and any specific study Data Monitoring Plan that is in place. In addition, source documents will be reviewed for accuracy against data found on the CRFs.

11.3 Device Accountability

Device accountability will be maintained by the Investigational Site. [REDACTED]

11.3.1 Returning used devices to SPR Therapeutics

The site will record any devices returned to SPR Therapeutics in the Device Accountability Log. The site will contact SPR to obtain a Return Goods Authorization (RGA) number prior to returning any devices.

Stimulators and Components

Disposal of all System components must comply with national and local laws governing the disposal of biohazardous waste. [REDACTED]

12.0 Adverse Events and Unanticipated Adverse Device Effects

Adverse events (AEs) that occur during the study will be captured on CRFs. Specific details regarding any observed AE will be collected on a separate Adverse Event Form. The severity of each Adverse Event will be collected as well as its relationship to the System. AEs will be classified as mild (event that causes mild discomfort or inconvenience and resolves without treatment), moderate (event that requires medical intervention or medication to treat), or severe (event that requires intervention to prevent permanent impairment or damage, an event that requires or prolongs hospitalization, or an event that is disabling, causing permanent damage, life threatening, or causing death). Adverse events will also be classified as serious or non-serious. Any necessary treatment or intervention required and the resolution status of the adverse event will also be documented. Adverse Events will be followed to resolution. Side effects from narcotic therapy will be collected but not reported as adverse events. Common symptoms after TKA surgery related to the normal healing process (i.e., swelling, bruising, stiffness, incision tenderness, drainage, etc.) will also not be reported as adverse events unless they meet the definition and criteria for AE reporting

An Adverse Device Effect (ADE) is a device-related Adverse Event. All ADE's are further categorized as anticipated or unanticipated. Any ADE's specified in the Risk Analysis of this Investigational Plan will be considered "anticipated". All other ADE's are considered "unanticipated". Anticipated events that occur with a greater frequency than expected are also considered unanticipated.

An Unanticipated Adverse Device Effect (UADE) is defined as any serious adverse effect on health or safety or any life threatening problem or death caused by, or associated with, a device, if that effect, problem or death was not previously identified in nature, severity or degree of incidence in this Investigational Plan or application or any other unanticipated serious problem associated with a device that relates to the rights, safety or welfare of subjects.

Table 2 Unanticipated Adverse Device Event Sponsor Contact Information

UNANTICIPATED ADVERSE DEVICE EVENT SPONSOR CONTACT INFORMATION			
Name/Title	Email address	Telephone Number	Fax Number
[REDACTED]	[REDACTED]	[REDACTED]	[REDACTED]
[REDACTED]	[REDACTED]	[REDACTED]	[REDACTED]
[REDACTED]	[REDACTED]	[REDACTED]	[REDACTED]

It is the responsibility of the investigator to inform his/her Institutional Review Board (IRB) of any ADEs and UADEs as required by the IRB. In addition, some IRBs will require that AEs that are serious in nature, even if not device related, will be reported as well. SPR Therapeutics is responsible for furnishing the required information to the appropriate regulatory authorities.

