Exclusion Criteria	
 • Body Mass Index (BMI) > 40 kg/m² • Conditions that place the subject at increased risk of infection in the opinion of the investigator, [REDACTED] • History of valvular heart disease • Implanted cardiac pacemaker/defibrillator or Deep Brain Stimulator • Bleeding disorder OR INR ≥ 1.5 for those on warfarin (Group #1, only) • Confounding conditions [REDACTED] [REDACTED] or central nervous system disorders • History of nerve damage [REDACTED] • Allergy to skin surface electrodes and/or medical-grade adhesive tapes • Contraindications to the proposed anesthetic protocol during lead placement [REDACTED] • Any other medical condition that may interfere with ability to participate in a clinical trial as determined by the Investigator • Prisoners, minors or individuals that report to investigators (e.g., students, employees) • Pregnant (Group #1, only) • History of substance abuse within 6 months • Potential secondary gain issues (e.g., pending claims or receiving disability)
Primary Safety Endpoint	Occurrence of device-related adverse events.
Primary Clinical Endpoint	
The primary clinical endpoint is average daily pain while walking. Subjects will record [REDACTED] pain while walking [REDACTED] in a daily diary [REDACTED]
 
[REDACTED] The difference in the [REDACTED] pain scores between the two groups (Treatment vs. Control) will be calculated to determine if PNS Therapy provides a [REDACTED] reduction in [REDACTED] daily pain while walking.

Secondary Endpoints	Pain-related outcomes

	
 • Pain intensity over the last 24 hours as recorded as Average pain [REDACTED] • Pain intensity [REDACTED] • Pain right now [REDACTED] • Cumulative analgesic usage [REDACTED] • Opioid-related side effects [REDACTED] 
Functional outcomes
 
 • Timed Up and Go [REDACTED] • 6 minute walk test [REDACTED] • Change in pain, physical function, and stiffness [REDACTED] • Patient Global Impression of Change (PGIC) [REDACTED] • Pain Catastrophizing Scale (PCS) [REDACTED] • Time to meet recovery milestones [REDACTED] • [REDACTED] 
Subject Satisfaction Survey
 
 • Inpatient Pain Management Experience Survey [REDACTED] • Compliance [REDACTED] • [REDACTED] 
Physical Therapy Sessions

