5.5 Safety Endpoint

The primary safety endpoint is the occurrence of protocol-related adverse events.

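### Section 12.0 records adverse-event causality only against the System, so the protocol-related safety endpoint in Section 5.5 cannot be derived from the attribution item the plan specifies

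*Combined protocol and SAP*

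**What the plan says.** **Causality item.** Section 12.0 of the combined protocol and SAP states: "The severity of each Adverse Event will be collected as well as its relationship to the System". No other relationship item appears in the readable text.

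**What depends on it.** The same section defines the device-effect class: "An Adverse Device Effect (ADE) is a device-related Adverse Event". Only events in that class are split into anticipated and unanticipated. The investigator's duty is to "inform his/her Institutional Review Board (IRB) of any ADEs and UADEs as required by the IRB".

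**The endpoint, stated twice.** The synopsis gives the primary safety endpoint as "Occurrence of device-related adverse events". Section 5.5 says: "The primary safety endpoint is the occurrence of protocol-related adverse events".

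**Study-only procedures in Group #1.** Section 8.5.2 limits the lead placement visit to Group #1 and allows it to be repeated. Sections 8.5.10 and 8.9 foresee lead replacement. The synopsis study plan has the leads taken out when treatment ends. An exclusion criterion in the synopsis shows that placement has its own anaesthetic: "Contraindications to the proposed anesthetic protocol during lead placement".

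**What is kept for every event.** Section 12.0 also says: "Adverse events (AEs) that occur during the study will be captured on CRFs". Section 10.3 plans to report and categorise adverse events without restricting this to related ones.

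**The concern.** Protocol-related is a wider class than device-related. It takes in events caused by what the study does to subjects, including inserting and removing leads and the anaesthetic used for placement, even when the device works as intended. An investigator asked only about the System could reasonably answer no for a reaction to the anaesthetic or a purely procedural complication. Nothing else the plan specifies would then mark that event as study-caused rather than due to the knee replacement or to ordinary care.

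The stake is the count for the primary safety endpoint. The lead procedures happen in one arm only, so any undercount falls on the PNS arm. With about 50 subjects in total, a handful of events decides how the safety result reads.

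**Working it through.** The plan gives no figure to reproduce, and the point does not depend on one. The check sets the text side by side and follows one event through it.

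**Step 1: which event is at issue.** Take a non-serious event in Group #1 caused by the placement anaesthetic, or by insertion or removal of a lead, with the device functioning normally. The investigator judges it unrelated to the System.

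**Step 2: follow it through the plan.**

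| Place in the plan | Condition for inclusion | Is the event included? |
|---|---|---|
| CRF capture, Section 12.0 | Any adverse event | Yes |
| Safety reporting, Section 10.3 | Any adverse event | Yes |
| Adverse device effect, Section 12.0 | Device-related | No |
| Anticipated/unanticipated split, Section 12.0 | Adverse device effect | No |
| Unanticipated adverse device effect, Section 12.0 | Serious, and caused by or associated with a device | No, because it is not serious |
| Primary safety endpoint, synopsis | Device-related | No |
| Primary safety endpoint, Section 5.5 | Protocol-related | Should be, but no specified item identifies it |

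The last row is the defect. Under the synopsis wording, the collected item and the endpoint broadly agree. Under Section 5.5 they do not: System-related events are a subset of protocol-related events, and the remainder cannot be picked out.

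**Step 3: how far the gap extends.** Section 13.2 lists lead exit-site irritation or infection, lead breakage, and discomfort or increased pain. Section 13.3 speaks of these as risks of using the system, so many lead events would probably be scored as related. What remains is mainly non-serious anaesthetic or purely procedural events.

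**Step 4: scale, on assumed numbers only.** Enrolment is up to 50 (Section 7.2), and no allocation ratio is readable. Assume 1:1, giving 50/2 = 25 in Group #1, or 2:1, giving 50 × 2/3 ≈ 33. Suppose two subjects each have one procedure-caused event, scored unrelated to the System, and no other subject has a qualifying event. Exact (Clopper-Pearson) 95% intervals are:

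| Assumed Group #1 size | Events counted | Events not counted |
|---|---|---|
| 25 | 2/25 = 8.0% (1.0 to 26.0) | 0/25 = 0% (0 to 13.7) |
| 33 | 2/33 = 6.1% (0.7 to 20.2) | 0/33 = 0% (0 to 10.6) |

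The upper limit for zero events is 1 − 0.025^(1/n): 1 − 0.025^(1/25) = 13.7% and 1 − 0.025^(1/33) = 10.6%. The table shows how sensitive a small trial is to two events. It does not estimate how many will be misclassified.

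**The case against.** A reader might infer that these events vanish from the safety result, that attribution is not collected at all, and that nothing could be done after database lock. The documents support none of the three.

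- Every adverse event goes on the CRF with severity, seriousness, treatment and outcome, and further details go on a separate Adverse Event Form. Section 10.3 reports events whatever their relationship. Because there is a randomised control arm, an all-event comparison would also reflect an excess in Group #1.
- The Adverse Event Form is not available for review, and much of the device description, visit procedures and risk list is blacked out. A fuller causality item may exist. Section 5.5 itself suggests that a protocol-relationship judgement is intended.
- Placement precedes the knee replacement, and Section 8.5.2 refers to a telephone check at 24 to 48 hours. Timing would therefore help to separate early placement events from surgical ones.
- Serious events are better covered. The unanticipated-effect definition takes in "any serious adverse effect on health or safety or any life threatening problem or death caused by, or associated with, a device", and Section 12.0 notes that some IRBs require serious events that are not device related. Reporting to the IRB already follows what the IRB asks for, so there is no case here for changing those duties.

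These arguments narrow the point to the endpoint count and the device-effect class. They do not remove it. An all-event comparison in about 50 subjects does not yield a count of protocol-related events. Timing does not separate lead removal, which follows the knee replacement, from surgical recovery. An intention implied by Section 5.5 is not an item that sites are told to complete.

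**Conclusion.** The point holds in this limited form. As written, the plan cannot identify an event that is protocol-related but not System-related, so the Section 5.5 endpoint cannot be derived from the causality item in Section 12.0. The synopsis avoids the difficulty only by defining a different endpoint. The consequence is a possible understatement of PNS-related risk in Group #1, confined to the primary safety endpoint count and the adverse-device-effect class, and mainly to non-serious anaesthetic or procedural events.

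Its size cannot be estimated from the documents. The 8.0% to 0% shift rests on an assumed 1:1 split and two assumed misclassified events. The conclusion also assumes that neither the Adverse Event Form nor the blacked-out text holds a further relationship item. If either does, what remains is to align Section 12.0 with it and to reconcile the two endpoint statements.

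**What to change.** 1. In Section 12.0 and on the Adverse Event Form, record relationship separately to (i) the SPRINT System; (ii) lead placement, replacement or removal, including the anaesthetic; (iii) other study procedures; and (iv) the TKA and standard of care.
2. Reconcile the synopsis and Section 5.5 to a single primary safety endpoint definition, and state which of these categories count toward it.
3. In the safety tables, report (i) to (iii) together as protocol-related, and show (i) and (ii) separately as well.

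The cost is a few extra items on an existing form and added lines in the safety table. The small downside is that slightly more events will count as study-related.

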5.3 Secondary Outcomes

Secondary outcome measures will provide additional information on pain and function.

The [REDACTED] is a widely used assessment designed to measure pain intensity and the interference of pain on daily activities and moods [REDACTED]

Cumulative Analgesic usage

The amount and type of analgesic used by the subject will be recorded daily in a diary before TKA surgery, from the subject's records during their hospital stay, in daily diaries after discharge from the hospital, and at each visit following End of Treatment.

Opioid-related Side Effects

Opioid pain medications are associated with a wide variety of side effects. Common side effects include nausea and vomiting, constipation, urinary retention, pruritus, drowsiness, and respiratory depression.

Timed Up and Go [REDACTED]

The [REDACTED] is an objective measure of mobility. [REDACTED]

Six minute walk test [REDACTED]

The [REDACTED] records the total distance the subject can walk in 6 minutes. [REDACTED]

The [REDACTED] is a widely-used validated questionnaire to evaluate patients with osteoarthritis of the knee and consists of 24 items evaluating pain (5 items), stiffness (2 items), and physical functional disability (17 items) [REDACTED]

Patient Global Impression of Change (PGIC)

Participant ratings of global improvement are one of the core outcome domains in chronic pain studies (Dworkin *et al.* 2005). [REDACTED]

Pain Catastrophizing Scale (PCS)

The PCS is a widely-used, validated and reliable 13-question instrument to assess rumination (4 questions), magnification (3 questions), and helplessness (6 questions) (Sullivan, 2009.; Osman *et al.* 1997). [REDACTED]

Time to Meet Recovery Milestones

The time until the subject meets criteria related to hospital discharge will be measured. [REDACTED]

Subject Satisfaction Survey

A survey will be administered to assess subject satisfaction with the study and postsurgical pain therapies.

Inpatient Pain Management Experience Survey

This survey is comprised of a subset of questions from the Hospital Consumer Assessment of Healthcare Providers and Systems. This survey will be administered to assess subject satisfaction with pain management during their time in the hospital for TKA surgery.

Compliance

SPRINT Beta stimulator [REDACTED]

[REDACTED] subject compliance [REDACTED]

Physical Therapy Sessions

[REDACTED] physical therapy sessions

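### The adverse event exemption for narcotic side effects in Section 12.0 has no exception for serious events

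*Combined protocol and SAP*

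**What the plan says.** Section 12.0 has two exemptions, one after the other. The first concerns opioids: "Side effects from narcotic therapy will be collected but not reported as adverse events". The second concerns ordinary recovery symptoms after the operation, such as swelling and bruising. These "will also not be reported as adverse events unless they meet the definition and criteria for AE reporting".

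The same section sets out what happens to an event that does count as an adverse event:
- On recording the event: "Specific details regarding any observed AE will be collected on a separate Adverse Event Form".
- On how serious it is: "Adverse events will also be classified as serious or non-serious".
- On how long it is followed: "Adverse Events will be followed to resolution".
- On grading it and linking it to the device: "The severity of each Adverse Event will be collected as well as its relationship to the System".

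Section 10.3 builds the safety analysis on adverse events as Section 12.0 defines them. Section 5.3 makes opioid side effects a secondary outcome and describes them thus: "Common side effects include nausea and vomiting, constipation, urinary retention, pruritus, drowsiness, and respiratory depression". Section 10.1 has subjects taking opioids queried about these effects and compares the results between groups.

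**The concern.** Exempting expected opioid effects such as nausea or constipation keeps the adverse event log readable, and that is reasonable. The difficulty is that the exemption depends only on attribution to narcotics and not on how serious the event is. The class it covers includes respiratory depression by the plan's own list.

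If a site follows the sentence literally, a serious event attributed to narcotics leaves adverse event handling at the moment of attribution. It could go without a seriousness classification or required follow-up, and could be absent from the safety summary.

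In Group #1 the order of decisions adds a further problem. Relationship to the System is collected for adverse events. An event first attributed to narcotics has therefore left that process before any visible text asks whether stimulation played a part. Subjects on stimulation may also be taking opioids, so the attribution is a judgement and can be wrong.

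**Working it through.** The documents give no figure to reproduce and no event rate, so the check is a reading of the text in three steps.

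**1. The two exemptions compared**

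| Class of event | Exempt from adverse event reporting | Exception stated |
|---|---|---|
| Narcotic side effects | Yes | None |
| Ordinary recovery symptoms after knee replacement | Yes | Yes: "will also not be reported as adverse events unless they meet the definition and criteria for AE reporting" |

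One of the two exemptions lacks an exception. In the second sentence the exception refers back to that sentence's own subject, the recovery symptoms. The word linking the two sentences joins the exclusions; it does not carry the exception back across a full stop.

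**2. Which safeguards depend on adverse event status**

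| Safeguard | Where | Groups affected if the event is exempt |
|---|---|---|
| Adverse Event Form | 12.0 | Both |
| Serious or non-serious classification | 12.0 | Both |
| Follow-up to resolution | 12.0 | Both |
| Inclusion in the safety summary | 10.3, which relies on 12.0 | Both |
| Relationship to the System | 12.0 | Group #1 only (7.2: only Group #1 receives stimulation) |

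That is 4 safeguards in both groups plus 1 in Group #1, or 4 + 1 = 5. All five follow from a single fact, the loss of adverse event status. The count shows what is affected and does not measure frequency.

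**3. Whether another route brings a serious narcotic event back in**

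- *Adverse device effect (12.0).* This is defined as a type of adverse event related to the device, so it presupposes the status that the exemption removes.
- *Unanticipated adverse device effect (12.0).* This covers "any serious adverse effect on health or safety or any life threatening problem or death caused by, or associated with, a device", subject to its not having been previously identified in the plan or application. It does not presuppose adverse event status, so it is a genuine but partial backstop. It needs a recognised link to the device, and it does not serve Group #2.
- *IRB reporting (12.0, after Table 2).* Serious events unrelated to the device go to the IRB where a given IRB requires it, and the sentence is written for events already counted as adverse events.
- *Secondary outcome (5.3, 10.0, 10.1).* The effects are collected, compared and reported. No visible text adds a seriousness classification or follow-up to resolution.

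No visible route closes the gap for a serious event attributed to narcotics alone.

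**The case against.** The strongest objection is that part of the relevant text cannot be seen. The exception in the second sentence refers to a definition and criteria for adverse event reporting that do not appear in the visible text. Opioid wording is redacted in several places, the in-hospital visit content is not shown, and Appendix A is not available. Any of these might settle the matter. This stands as a limit: the finding is about what the visible text requires, and the sponsor may be able to point to a provision elsewhere.

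A second objection is that the two exemptions were meant as a pair, with one exception closing both. That may be the intent, but the wording does not say so. A site should not have to guess.

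A third is that little is lost. The effects are still collected and analysed, and an event truly caused by narcotics is not related to the device. It would therefore not enter the primary safety endpoint as the synopsis words it (Section 5.5 refers instead to events related to the protocol). This is largely right and keeps the concern modest. It does not cover a misattributed event in Group #1, nor does it supply classification and follow-up in either group.

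It is also fair to say that no visible text defines a serious event; only mild, moderate and severe are defined. Section 12.0 nevertheless already requires the serious or non-serious classification, so an exception based on it asks for no new concept.

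**Conclusion.** The concern holds on the visible text. Section 12.0 removes narcotic side effects from adverse event reporting without regard to seriousness, and no visible passage restores the serious ones. Four adverse event safeguards lapse in both groups and a fifth in Group #1.

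The frequency of such events is unknown and no expected number is claimed. The gap is in classification, follow-up and safety reporting; the data are still captured. It does not alter the primary outcome, pain while walking. The change should be made because it protects subjects at small cost, but the trial's main result does not depend on it. Confidence is medium, because the conclusion assumes that the redacted and unavailable text contains no exception for serious events.

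**What to change.** Add one clause to the narcotic sentence in Section 12.0: these side effects are collected but not reported as adverse events unless they meet the sponsor's definition of serious. Those that do are reported as adverse events, with the form, the follow-up to resolution and, in Group #1, the assessment of relationship to the System that Section 12.0 already prescribes. They then enter the Section 10.3 summary without further change. Non-serious opioid effects stay as a secondary outcome only, with no added relatedness test.

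The clause should point to where the sponsor defines serious. If an exception already exists in text not shown here, or if the existing exception was meant to cover both sentences, the sponsor should say so in Section 12.0.

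The cost is one clause, plus a form and follow-up for each serious event attributed to narcotics. The documents do not allow that number to be estimated. Non-serious effects add no work.
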